The Add-On Effect of Lactobacillus plantarum PS128 in Patients With Parkinson's Disease: A Pilot Study

NCT04389762

December 31, 2021

1. Assessment of Outcomes

In this study, the primary measurements were the Unified Parkinson's Disease Rating Scale part III (UPDRS-III) motor scores and changes in patient's "ON-OFF" diary recordings, and modified Hoehn and Yahr scale (mHYS). The secondary measurements were the 39-item Parkinson's Disease Questionnaire (PDQ-39), Non-Motor Symptoms Scale (NMSS), BDI-II, patient assessment of constipation symptoms (PAC-SYM), Patient Global Impression of Change (PGI-C), and other metabolic profiles. All clinical assessments were performed after 12 h of overnight withdrawal from antiparkinsonian medications (24 h of withdrawal was needed if the participants were taking prolonged release dopaminergic agonists). Therefore, UPDRS-III and mHYS were scored in the OFF state the next morning as well as the metabolic profiles. Then, the medications were self-administered by each patient before the secondary measurements. The UPDRS, mHYS, PDQ-39, NMSS, BDI-II, PAC-SYM, and PGI-C were scored 40–60min later in the patients' best ON state. For safety assessment, physical and neurological examinations were performed to evaluate the overall health of the subjects at weeks 0 and 12. In addition, all subjects were actively monitored for the occurrence of adverse events by telephone at least once per week.

2. Biochemical Measurements

A blood sample of 15mL and a urine sample of 10mL were collected at weeks 0 and 12. The serum high-sensitivity C-reactive protein level was determined by turbidimetric immunoassay. The plasma myeloperoxidase (MPO) and urinary 8-hydroxy-2'-deoxyguanosine were measured by enzyme-linked immunosorbent assay. The plasma glutathione peroxidase and total antioxidant capacity were measured by Ransel test kits (Randox Laboratories Ltd., UK) and ferric-reducing ability, respectively. The urinary creatinine (CRE) level was determined by MeDiPro creatinine test. All procedures were performed according to the manufacturer's

instructions.

3. Statistics Analysis

For this clinical trial, all statistical analyses are conducted using SPSS software (Version 22.0, IBM Corp., Armonk, NY). Descriptive statistics are presented as mean \pm standard deviation (SD). The Wilcoxon signed-rank test is used for comparisons on ordinal scales when a significant difference is observed. This test is employed to evaluate changes in total UPDRS, UPDRS-I, UPDRS-II, UPDRS-III, UPDRS-IV, as well as subscores for tremor, rigidity, akinesia, and postural instability gait disorder (PIGD), mHYS, diary recordings, PDQ-39, BDI-II, and PAC-SYM from baseline (V0) to post-intervention (V1, 12 weeks). Effect sizes are calculated using Cohen's d, defined as the mean change divided by the SD. For nominal scale variables with significant differences, the chi-square test is applied, particularly for the NMSS. Paired Student's t-test is used to assess differences in metabolic parameters between baseline and after the probiotics intervention. All data are reported as the mean \pm SD, with statistical significance set at $p < 0.05$.

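### The Wilcoxon and chi-square tests are made conditional on a significance no named test supplies; the Wilcoxon list contradicts its condition, but NMSS is left without a clearly unconditional test

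*Combined protocol and SAP*

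**What the plan says.** Section 3 (Statistics Analysis) names three tests.

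- **Wilcoxon signed-rank.** The general rule is: "The Wilcoxon signed-rank test is used for comparisons on ordinal scales when a significant difference is observed". The sentence after it begins "This test is employed to evaluate changes in total UPDRS, UPDRS-I, UPDRS-II, UPDRS-III, UPDRS-IV" and goes on to four motor subscores, mHYS, diary recordings, PDQ-39, BDI-II and PAC-SYM, compared between V0 and V1. That second sentence has no condition of its own.
- **Chi-square.** "For nominal scale variables with significant differences, the chi-square test is applied, particularly for the NMSS". No later sentence adds to this, and it does not name the time points compared.
- **Paired t-test.** "Paired Student's t-test is used to assess differences in metabolic parameters between baseline and after the probiotics intervention". This carries no condition.

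Two reporting sentences are also unconditional: "Effect sizes are calculated using Cohen's d, defined as the mean change divided by the SD", and "All data are reported as the mean" with SD. The 0.05 threshold is given once and is not attached to any preliminary test.

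Section 1 (Assessment of Outcomes) sets the status of the outcomes. It states that "the primary measurements were the Unified Parkinson's Disease Rating Scale part III (UPDRS-III) motor scores", together with the diary recordings and mHYS. PDQ-39 heads the secondary measurements, followed by "Non-Motor Symptoms Scale (NMSS), BDI-II, patient assessment of constipation symptoms (PAC-SYM), Patient Global Impression of Change (PGI-C") and metabolic profiles.

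**The concern.** A significance test is run to find out whether a change is significant. A rule that calls for the test only once significance has been seen needs an earlier test to supply that significance, and section 3 names none. Read literally, the rule is either circular or confines testing to outcomes already judged significant by some undisclosed means.

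At stake is whether the plan fixes, before results are seen, which outcomes receive a p-value. The general Wilcoxon rule leaves that in doubt until the next sentence is read. For NMSS the doubt is never removed: a reader cannot tell whether its change from baseline will be tested regardless of how the data look.

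**Working it through.** The plan states no figure on this point, so the check is to set the sentences side by side and count.

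**1. Which test rules are conditional?** Wilcoxon: yes, in its general sentence. Chi-square: yes. Paired t-test: no. That is 2 of 3.

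**2. Could any named test supply the prior significance?** The only rule free of the condition is the paired t-test, and it is confined to metabolic parameters. For ordinal and nominal outcomes no omnibus, screening or first-stage test is named. Candidates: 0.

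**3. Which outcomes does the Wilcoxon list cover?**

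- UPDRS total and parts I to IV: 5
- tremor, rigidity, akinesia and PIGD subscores: 4
- mHYS, PDQ-39, BDI-II, PAC-SYM: 4
- diary recordings: 1

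5 + 4 + 4 + 1 = 14. All three primary measurements (UPDRS-III, diary recordings, mHYS) are among them. The plan never describes diary recordings as an ordinal scale, so the condition in the general sentence may not reach them in any case.

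**4. How do the two Wilcoxon sentences fit together?** There are two readings.

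- The list sentence stands on its own. All 14 outcomes are tested, and the condition in the preceding sentence is contradicted.
- The list sentence inherits the condition. The rule is then circular, because nothing else supplies the significance.

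The first is the more natural. A specific list usually governs a general lead-in, and the list sentence describes evaluating change between two visits, which is what the test does.

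**5. Does the same reasoning rescue NMSS?** Section 1 names five clinical secondary measurements: PDQ-39, NMSS, BDI-II, PAC-SYM and PGI-C. Three (PDQ-39, BDI-II, PAC-SYM) are on the Wilcoxon list. NMSS is not. There are two routes to a test for it.

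- As a nominal variable, which is where section 3 puts it: the chi-square sentence, which is conditional.
- As an ordinal scale: the general Wilcoxon sentence, which is also conditional, and NMSS is absent from the list that would lift the condition.

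Neither route reaches a clearly unconditional test. (PGI-C is named in no test at all; that is a separate matter.)

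**6. Would the condition raise the error rate?** Let W be a Wilcoxon result with p < 0.05, and S be passing some unnamed prior screen. If there is no true change and the Wilcoxon test holds its level, P(W and S) ≤ P(W) ≤ 0.05. Adding a hurdle cannot push the unconditional error for an outcome above 5%. How p-values would behave among outcomes that pass a screen cannot be worked out, because the plan describes no screen and gives no sample size.

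**The case against.** The strongest reply is that both clauses are loose drafting, meant to say that the tests determine whether a difference is significant. For the 14 listed outcomes this largely succeeds: the list sentence gives each a workable test between V0 and V1, the threshold is stated, and nothing in the documents hints at a real preliminary screen. What remains there is an internal inconsistency.

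The same charity can be extended to the chi-square sentence, which would then simply assign that test to NMSS. This is a fair reading, but it stands only in part. The Wilcoxon outcomes have a second sentence that supports it; NMSS has none. The restriction also appears twice, in different words, and is absent from the third rule, so it is hard to dismiss as a single slip.

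A reader might go further and infer that non-significant results will be withheld, that effect sizes will be inflated by selection, or that the false-positive rate will exceed 5%. The documents do not support any of these. The effect-size sentence is unconditional, mean and SD are promised for all data, and a screen could not raise the per-outcome error, as shown in the working. Any count of outcomes left untested would presuppose a screen that the plan does not describe.

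It can also be said that the choice between chi-square and a paired test for NMSS is a separate question. It is, and it adds no weight here. It arises only because a replacement NMSS sentence has to name some test, and that test should suit repeated measurements on the same patients.

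**Conclusion.** The point holds as a defect of wording with one substantive gap. Two of the three test rules depend on a significance that no named test provides.

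- **The 14 listed outcomes, including all three primary measurements: minor.** Two adjacent sentences conflict, the likely intent is to test all of them, and no bias or raised error rate is shown.
- **NMSS: the substantive part.** One of five named clinical secondary measurements has no clearly unconditional test of change from V0 to V1, and nothing elsewhere in the documents supplies one.

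This rests on the text of sections 1 and 3 alone. Confidence is high that the text is ambiguous. It does not extend to any practical effect on results, because the intended procedure cannot be established from these documents.

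**What to change.** In section 3:

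1. Delete the conditional clause from the Wilcoxon sentence and from the chi-square sentence.
2. State that every listed outcome is tested for change from V0 to V1 with the Wilcoxon signed-rank test.
3. State the form in which NMSS is analysed, and that its change from V0 to V1 is tested unconditionally with a paired test: Wilcoxon signed-rank if it is a score, McNemar if it is a set of yes/no items.
4. State that the p-value is reported for every outcome, whatever the result.

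The paired t-test rule needs no change on this point. If a preliminary screen was in fact intended, the plan should instead name that test and its significance level.

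Cost: two clauses of wording, one decision on the form of NMSS, and a slightly longer results table. No new data are needed.

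### The NMSS, a scored secondary scale, is treated as nominal and given an unspecified chi-square test instead of the paired Wilcoxon test used for PDQ-39, BDI-II and PAC-SYM

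*Combined protocol and SAP*

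**What the plan says.** Section 1 (Assessment of Outcomes) lists the NMSS among the secondary measurements and describes how it was obtained: "The UPDRS, mHYS, PDQ-39, NMSS, BDI-II, PAC-SYM, and PGI-C were scored 40–60min later in the patients' best ON state". It mentions no nominal coding, cut-off or present/absent grouping.

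Section 3 (Statistics Analysis) gives the rule for ordinal scales: "The Wilcoxon signed-rank test is used for comparisons on ordinal scales when a significant difference is observed". The variables under that rule end with "mHYS, diary recordings, PDQ-39, BDI-II, and PAC-SYM from baseline (V0) to post-intervention (V1, 12 weeks". The NMSS is not among them. It appears two sentences later: "For nominal scale variables with significant differences, the chi-square test is applied, particularly for the NMSS". Metabolic parameters get a paired t-test. The section closes with a general reporting rule that begins "All data are reported as the mean", with SD.

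**The concern.** The two sections disagree on what kind of variable the NMSS is. Section 1 treats it as a score, like PDQ-39, BDI-II and PAC-SYM. Section 3 treats it as nominal and takes it off the paired list without giving a reason.

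The comparisons that section 3 spells out are baseline against week 12 in the same patients, and no control arm is described. I therefore infer that the NMSS comparison is also within patient. An unspecified chi-square can then mean three different things:

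1. Pearson chi-square on visit by category. Each patient is counted twice and the pairing is ignored.
2. Pearson chi-square on baseline category by week-12 category. This tests whether the two visits are associated, not whether patients changed.
3. McNemar's test. This is a valid test of paired change, but the plan does not name it, and it reduces the score to a yes/no variable.

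These give different p-values with different meanings. A reader could not set the NMSS result beside those of the other secondary scales.

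**Working it through.** **Text check.** Set side by side:

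| Scale | Section 1 | Test in section 3 |
|---|---|---|
| PDQ-39 | secondary, scored in ON state | Wilcoxon signed-rank, V0 to V1 |
| BDI-II | secondary, scored in ON state | Wilcoxon signed-rank, V0 to V1 |
| PAC-SYM | secondary, scored in ON state | Wilcoxon signed-rank, V0 to V1 |
| NMSS | secondary, scored in ON state | chi-square, type not stated |
| PGI-C | secondary, scored in ON state | none named |

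Nothing else in the documents explains why the NMSS is handled differently.

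**Inputs for the illustration.** The plan gives only the 0.05 significance level; I take it as two-sided. It has no NMSS figure to reproduce. Everything else is assumed: n = 25 (range 15 to 40), V0–V1 correlation r = 0.7 (0.5 to 0.8), a bivariate-normal underlying score, and a dichotomy with 60% symptom-present (50% to 80%).

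**No true change, central case.** With 60% present at both visits and r = 0.7, the paired cell probabilities are: present at both 0.478, present at V0 only 0.122, present at V1 only 0.122, absent at both 0.278. The correlation between the two yes/no variables is φ = (0.478 − 0.60²)/(0.60 × 0.40) = 0.118/0.24 ≈ 0.49.

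- *Visit by category.* Pearson assumes a variance of 2 × 0.60 × 0.40/n = 0.48/n for the difference in proportions. The true variance is (0.122 + 0.122)/n ≈ 0.245/n, a ratio of 0.51. The test statistic therefore has SD √0.51 ≈ 0.71 instead of 1, and the test rejects too rarely. Exact enumeration of the 2×2 table gives 0.9%.
- *V0 by V1.* The statistic is n times the squared sample φ, so it is centred near 25 × 0.49² ≈ 6.0, against a critical value of 3.84, although nothing has changed. Exact rejection is 71.6%.
- *McNemar, uncorrected:* (b − c)²/(b + c), where b and c are the two discordant counts. Exact rejection is 4.8%.
- *Wilcoxon on the score:* about 5% by simulation.

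Over the assumed ranges, the rejection rates are 0.3–2.4% (visit by category), 23–98% (V0 by V1) and 1.6–5.0% (uncorrected McNemar). At 60% prevalence the V0-by-V1 figure is below 50% in three of the nine n-by-r combinations: 24% at n = 15, r = 0.5; 48% at n = 15, r = 0.7; and 39% at n = 25, r = 0.5.

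**Power at n = 25, r = 0.7** (dichotomised tests by exact enumeration, Wilcoxon by simulation):

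| Shift in score | Wilcoxon | McNemar, uncorrected | McNemar, mid-p | McNemar, exact | Visit by category |
|---|---|---|---|---|---|
| 0.52 SD (70% to 50%) | 88–89% | 47% | 43% | 31% | 28% |
| 0.4 SD | 67% | 30% | 27% | 17% | 15% |
| 0.3 SD | 44% | 19% | 16% | 9% | 8% |

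The first Wilcoxon entry is a range because two simulation runs gave 0.883 and 0.886. The V0-by-V1 chi-square rejects 66% of the time at the 0.52 SD shift, less often than with no change (72%), so in this case its significance carries no useful information about change.

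**Source of the loss.** The share due to dichotomising is (Wilcoxon − McNemar)/(Wilcoxon − visit chi-square). With uncorrected McNemar it is (0.886 − 0.466)/(0.886 − 0.276) = 0.69 at 0.52 SD, (0.672 − 0.297)/(0.672 − 0.145) = 0.71 at 0.4 SD and (0.440 − 0.187)/(0.440 − 0.075) = 0.69 at 0.3 SD. With mid-p McNemar it is 0.74 to 0.77. The rest comes from ignoring the pairing.

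**The case against.** The best reply is that the plan is ambiguous, not demonstrably wrong. McNemar's test is itself a chi-square test, the authors may have meant it, and section 3 does not say that the NMSS test is V0 against V1. This stands in part: the invalidity applies to an ordinary chi-square, and the within-patient comparison is inferred. But McNemar also needs a defined yes/no variable, which the plan does not give, and even then the test is much weaker than Wilcoxon on the score.

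Second, the visit-by-category test never exceeded the nominal 5% over the assumed grid. That is correct: it misses real change and does not manufacture findings.

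Third, the 72% figure depends on a V0-by-V1 table that nothing in section 3 points to. That is also fair. It shows what one reading would do, and the case for a change does not need it.

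Fourth, the reporting of everything as a mean is a general sentence and only weak evidence about the NMSS, and PGI-C has no named test, so not every companion scale is on the Wilcoxon list. Both points are right, but neither explains the contrast with PDQ-39, BDI-II and PAC-SYM.

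Finally, this is one secondary outcome in a pilot, and every magnitude rests on assumptions. I agree, and that limits the severity.

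**Conclusion.** The concern holds and should be fixed. The inconsistency is certain from the text: a scored secondary scale is labelled nominal and sent to an undefined chi-square, while three comparable scales get a paired test.

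The consequence depends on which chi-square was meant. One reading is conservative and weak, one does not address change, and one is valid but discards the score. None of them is as good as the test the plan already uses for the comparable scales. In the central illustration, replacing Wilcoxon by a dichotomised test costs about 25 to 61 percentage points of power across the three shifts, for uncorrected McNemar or the visit-by-category chi-square. For the smallest loss, 44 − 19 = 25; for the largest, 0.886 − 0.276 = 0.61. These figures rest on the assumed n, correlation and prevalence and on a normal underlying score; they are not estimates for this trial. The primary measurements (UPDRS-III, diary recordings and mHYS) are not touched.

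**What to change.** In section 3, add the NMSS to the Wilcoxon signed-rank list with PDQ-39, BDI-II and PAC-SYM, and say whether the total score, the domain scores or both are tested. Delete the reference to the NMSS from the chi-square sentence. Keep the rest of that sentence only if it states which variables it covers, and give a paired test to any of them that is compared within patients between V0 and V1.

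If a present/absent analysis of NMSS symptoms is also wanted, define the dichotomy in advance and name the version of McNemar's test. Mid-p is preferable to exact at small n: in the illustration, exact McNemar gains almost nothing over the visit-by-category chi-square (31% against 28% at the largest shift).

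The cost is one or two sentences of wording and a rerun in the same software with a test already in the plan. No new data are needed. If NMSS results have already been produced, report which chi-square was used and label the Wilcoxon result as a change to the plan.
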